2.4.2 Multiple testing strategy

To control the overall type I error rate, the primary endpoint and secondary efficacy endpoints will be tested in sequence as follows:

1. The primary endpoint will be tested at 2-sided significance level $\alpha=0.05$.
2. If a statistically significant result is obtained for the primary endpoint (test 1), change from baseline in WB longitudinal composite MFI in B muscles at Week 48 and relative change from baseline in average shoulder abductor strength by hand-held quantitative dynamometry at Week 48 will be tested using the Bonferroni procedure, i.e., each will be tested at 2-sided $\alpha = 0.025$ (test 2).
 - If both tests are significant, a statistically significant result is obtained from test 2. The remaining significance level from test 2 = 0.05.
 - If only one of the 2 tests is significant, a statistically significant result is obtained from test 2. The remaining significance level from test 2 = 0.025.
 - If neither test is significant, a statistically significant result is not obtained from test 2.
3. If a statistically significant result is obtained from test 2, PGIC at Week 48 will be tested at the remaining significance level from test 2 (test 3).
4. If a statistically significant result is obtained from test 3, change from baseline in Neuro-QoL-UE at Week 48 will be tested at the remaining significance level from test 3, which is equal to the remaining significance level from test 2.

In recognition of the complexities of this rare disease and the novelty of this research field, in case the result of the primary analysis (MMRM) of the primary endpoint is on the boundary of statistical significance, but at least one of the following is true:

- results from most sensitivity analyses are nominally significant,
- result of PGIC at Week 48 is nominally significant,
- result of Change from baseline in WB longitudinal composite MFI in B muscles at Week 48 is nominally significant,

AND

- results from most of the remaining secondary and exploratory efficacy endpoints are directionally favorable to losmapimod,

the totality of evidence will be utilized to support the decision making.

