5. SAMPLE SIZE CONSIDERATIONS

The target population for this clinical trial is patients with FSHD1 and FSHD2. The clinical trial will reflect the current epidemiologic information about FSHD, with patients with FSHD1 making up approximately 95% of the study population and the other 5% being people living with FSHD2.

Assuming the within-group standard deviation (SD) of change is 0.08, a sample size of 210 patients with FSHD1 (105 patients per group) will be needed to provide at least 95% power with a 2-sided t-test at 0.05 significance level to detect a difference of 0.05 between losmapimod and placebo for the primary endpoint. An additional approximately 20 patients with FSHD2 will be recruited. The primary analysis will include patients with FSHD1 and FSHD2. Premature withdrawal and missing data are discussed in 9.1.

For the secondary efficacy endpoints of change from baseline in WB longitudinal composite MFI of B Muscles and PGIC at Week 48, assuming the within-group SDs are 0.72 and 1.0 respectively, a sample size of 210 patients with FSHD1 will provide at least 95% power with a 2-sided t-test at 0.025 significance level to detect a difference of 0.5 and 0.6 respectively between losmapimod and placebo.

For the secondary efficacy endpoint of relative change from baseline in average shoulder abductor strength at Week 48, assuming the within-group SD is 46, a sample size of 210 patients with FSHD1 will provide at least 75% power with a 2-sided Wilcoxon rank-sum test at 0.025 significance level to detect a difference of 20.2 between losmapimod and placebo.

In the above calculations, the assumed treatment differences and SDs are based on results from an ongoing Phase 2 study, Study FIS-002-2019 (ReDUX4). It is also assumed that 10% of the study population has missing Week 48 data. All power calculations were performed using the POWER Procedure of SAS[®] Version 9.4.

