9.3.1.5 MRI data

The objectives of the study relate to whole body longitudinal composite MFI and MFF. In addition, exploratory analyses are planned for whole body longitudinal composite lean muscle volume (LMV); analysis of each muscle MFI, MFF and LMV; and RWS cross-sectional composite MFI, MFF and LMV. MRI data are complex, and an intermediate step of derivation is carried out prior to statistical analysis. Derivations for this intermediate step may be found in Appendix C. The section below gives derivations relevant to the statistical analysis using the dataset that will be analyzed. These derivations are common to MFI, MFF and LMV endpoints.

Muscle categories

A, B, C muscle category codes are assigned to each muscle at baseline by the MRI vendor based on MFF and MFI and are applied throughout the study:

MFF Criteria		MFI criteria	Muscle Category	Code
MFF < 50%	and	MFI < 10%	Normal	A
MFF < 50%	and	MFI \geq 10%	Affected	B
MFF \geq 50%	-	-	End-stage	C

REACH TRIAL

where:

- A. Normal = a muscle that appears normal and is most likely not affected by disease.
- B. Affected = a muscle that is more likely to have disease involvement, but which still retains some functional capacity.
- C. End-stage = a muscle that is most likely to have loss of functional capacity.

Whole-body Longitudinal composite endpoints

These endpoints relate to measurements of change from baseline in LMV, MFI and MFF. These are specific to three muscle group categorizations: A, B, A+B. Note that baseline is measured during screening. If there is more than one screening measurement, then the last available assessment prior to first dose of treatment should be used. For the analysis of these endpoints four measures are required:

(1) Baseline whole body longitudinal LMV, MFI and MFF are variables with the label of type:

Lngrdl [Y] Ref Scrn [*Muscle categories included*] [*unit*]

where *Y*=MFI, MFF or LMV; *unit* = percentage points(pp) when *Y*=MFI or MFF; and *Muscle category included* = A, B, or A+B; and *unit* = liters (L) when *Y*=LMV; with Visit Name = 'Screening'.

(2) Change from baseline whole body longitudinal LMV, MFI and MFF are variables with the label of type:

Lngrdl [Y] Chng from Scrn [*Muscle categories included*] [*unit*]

where *Y*=MFI, MFF or LMV; *unit* = percentage points(pp) when *Y*=MFI or MFF; and *Muscle category included* = A, B, or A+B; and *unit* = liters (L) when *Y*=LMV; with Visit Name = '24 weeks' or '48 weeks'.

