Change from baseline validity: At weeks 24 and 48, reference LMV is assessed using reference screening LMV ($LMV(t)_{REF}$); and reference screening muscle count ($N(t)_{REF}$), where $t=24$ or 48 . $N(t)_{REF}$ is the total number of individual muscles assessed at time t . These are labelled in the raw data as:

Lngrdnl LMV Ref Scrn [*Muscle categories included*]

Lngrdnl LMV Ref Scrn Mscl Cnt [*Muscle categories included*]

If a patient's reference LMV is too small, then change from baseline should be coded as missing per instruction from the MRI vendor. $LMV(t)_{REF}$ is considered too small if:

- $LMV(t)_{REF} < 0.25L$ when $N(t)_{REF} \geq 2$; or
- $LMV(t)_{REF} < 0.5L$ when $N(t)_{REF} = 1$

(3) Reference screening whole body longitudinal LMV, MFI and MFF for a muscle group are measured at weeks 24 and 48. These are labelled:

Lngrdnl [Y] Ref Scrn [*Muscle categories included*]

REACH TRIAL

where *unit* = percentage points(pp) when $Y=MFI$ or MFF ; and *unit* = liters (L) when $Y=LMV$.

(4) Absolute whole body longitudinal LMV, MFI and MFF for a muscle group measured at weeks 24 and 48 are derived from Reference screening and Change from baseline as:

Absolute for Y = Reference screening for Y at time t + Change from baseline for Y at time t
where $Y=MFI$, MFF or LMV , and $t=24$ or 48 weeks.

Individual muscle measurements

There are 36 muscles measured, 18 on each side of the body:

- Infraspinatus
- Subscapularis
- Supraspinatus
- Teres Minor
- Biceps Brachii
- Deltoideus
- Triceps Brachii
- Latissimus
- Dorsi/Teres Major
- Pectoralis Major
- Rhomboideus
- Serratus Anterior
- Spinal Erectors
- Th1-Sacrum
- Trapezius
- Adductors
- Gastrocnemius
- Medialis
- Hamstrings
- Quadriceps
- Tibialis

LMV, MFI and MFF are measured for each muscle at screening, 24 and 48 weeks. These are labelled as:

[Muscle Name] [measurement Type] [Unit of Measurement]

E.g., "Left Infraspinatus Muscle Fat Fraction (MFF) [%]."

Change from baseline is derived at 24 and 48 weeks as defined in 9.2 above.

Missing data

All MRI missing data where a scan is known to have taken place will be queried prior to database lock. For signal quality issues, see Appendix C.

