10.2.2.2 Change from baseline in whole body (WB) longitudinal composite MFI (B muscles)

This endpoint will follow the same method of analysis as for the primary endpoint (see 10.2.1.1) using an MMRM. The primary analysis of this endpoint will be based on the MMRM. An LME will also be fitted as defined in 10.2.1.1, where the dependent variable is absolute WB composite MFI, measured at baseline and each post-baseline visit.

Additionally, this endpoint will be analyzed using the Wilcoxon rank-sum test, stratified by the FSHD repeat number category (see 8.2). The Hodges-Lehmann estimate of the associated treatment

REACH TRIAL

difference and asymptotic nonparametric 95% confidence interval will be computed. Median change from baseline will be plotted by treatment group.

A sensitivity analysis of this endpoint will be carried out based on the on-treatment measurements up to 2 days (inclusive) after the last dose of study drug for patients in the FAS. Another sensitivity analysis will adjust for correct FSHD repeat number category (see 10.2.1.2).

The analysis will be repeated for each subgroup listed in Section 8.5.

All WB longitudinal composite endpoint data and cross-sectional composite data (MFI/MFF/LMV) will be presented by patient in a listing, by FSHD type and treatment group.

10.2.2.3 Relative change from baseline in average shoulder abductor strength by handheld quantitative dynamometry at Week 48

This endpoint will be analyzed using the Wilcoxon rank-sum test, stratified by the randomization stratification factor (see 8.2). The Hodges-Lehmann estimate of the associated treatment difference and asymptotic nonparametric 95% confidence interval will be computed. Median relative change from baseline will be plotted by treatment group.

A sensitivity analysis of this endpoint will be carried out based on the on-treatment measurements up to 2 days (inclusive) after the last dose of study drug for patients in the FAS. Another sensitivity analysis will adjust for correct FSHD repeat number category (see 10.2.1.2).

The analysis will be repeated for each subgroup listed in Section 8.5.

All dynamometry data will be presented by patient in a listing, by FSHD type and treatment group.

[figure not shown]

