 - (Step 1) AMRA calculates the Week 24 **Reference Screening** values based on the set of muscles that are still eligible ($SI_{long} = 1$). (Note: if new signal quality issues are identified, the eligible muscle count will change and the Reference Screening values will be updated; otherwise, if the muscle count has not changed, the Reference Screening values at Week 24 remain the same as the initial study-level Reference Screening values at Screening). AMRA also refers to these as **Reference Timepoint 1 (TP1)** values and provides them as a set of 4 results: Reference Screening LMV muscle count, LMV_{tot} , MFI_{tot} , and MFF_{tot} .

- (Step 2) AMRA calculates the **Week 24** actual values based on the same set of muscles eligible at this visit. AMRA also refers to these as **Timepoint 2 (TP2)** values. Note: these TP2 results are interim values that AMRA uses for the calculations but does not directly provide them in the MRI data transfer to Fulcrum (see additional details below in the Section for Post-Data Transfer Processing Steps).
- (Step 3) AMRA derives the **Week 24 Change from Reference Screening** values using the Week 24 TP1 and TP2 values (from Steps 1 and 2 above). AMRA provides these change results in the data transfer as a set of 4 highly derived longitudinal composite results:
 - absolute change in LMV_{tot} (unit = L),
 - relative change in LMV_{tot} (unit = %),
 - absolute change in MFF_{tot} (unit = percentage points),
 - absolute change in MFI_{tot} (unit = percentage points).
- **At Week 48:** AMRA repeats the process (as noted above for Week 24) and provides a similar set of visit-level **Reference Screening** and **Change from Reference Screening** at Week 48 values in the data transfer to Fulcrum. Note: for the Week 48 visit, AMRA also includes an extra set of composites that are calculated using Week 24 as the Reference TP1 instead of Screening. However, for the double-blind placebo-controlled portion of the study, this extra set of Reference Week 24-as-TP1 results will not be used; only Reference Screening TP1-based results will be used for this portion of the study.

Longitudinal Composites: Post-Data Transfer Processing Steps

Once AMRA provides the highly derived longitudinal composite results, Fulcrum will perform some additional post-data transfer processing steps to prepare the longitudinal results for analysis.

Calculate Actual TP2 Analysis Values

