AMRA first identifies the longitudinal analysis set of **B Muscles** (i.e., muscles with $SI_{cat} = B$ at Baseline with $SI_{long} = 1$) and derives the composite measurements at each visit.

Absolute Change from Baseline in MFI_{tot} in B Muscles at Week 48 is described here using AMRA terminology and equations:

- Baseline MFI_{tot} = AMRA-derived Reference Screening TP1 value for MFI_{tot} at Week 48 (unit: %).
- Absolute Change from Baseline MFI_{tot} at Week 48 = AMRA-derived MFI_{tot} Change from Reference Screening at Week 48 value (unit: percentage points).

[figure not shown]
The equation AMRA uses to calculate absolute change in MFI_{tot} at Week 48 for B Muscles is:

$$\Delta MFI_{tot} = \frac{\sum_{i \in SI_{cat,tp1=B}} SI_{long,i}^{comb} \cdot MFI_{i,tp2} \cdot LMV_{i,tp2}}{\sum_{i \in SI_{cat,tp1=B}} SI_{long,i}^{comb} \cdot LMV_{i,tp2}} - \frac{\sum_{i \in SI_{cat,tp1=B}} SI_{long,i}^{comb} \cdot MFI_{i,tp1} \cdot LMV_{i,tp1}}{\sum_{i \in SI_{cat,tp1=B}} SI_{long,i}^{comb} \cdot LMV_{i,tp1}}$$

Note: AMRA uses SI_{long} values combined from both timepoints to ensure only reliable results from evaluable muscles with acceptable MRI signal quality are included:

REACH TRIAL

$$SI_{long}^{comb} = SI_{long,tp1} \cdot SI_{long,tp2}$$

Absolute change in LMV_{tot} (L):

$$\Delta LMV_{tot} = \sum_{i \in SI_{cat,tp1=B}} SI_{long,i}^{comb} \cdot (LMV_{i,tp2} - LMV_{i,tp1})$$

Relative change in LMV_{tot} (%):

$$\Delta LMV_{tot}^{relative} = \sum_{i \in SI_{cat,tp1=B}} SI_{long,i}^{comb} \cdot \left(\frac{LMV_{i,tp2} - LMV_{i,tp1}}{LMV_{i,tp1}} \right)$$

Absolute change in MFF_{tot} (pp):

$$\Delta MFF_{tot} = \left(1 - \frac{\sum_{i \in SI_{cat,tp1=B}} SI_{long,i}^{comb} \cdot LMV_{i,tp2}}{\sum_{i \in SI_{cat,tp1=B}} SI_{long,i}^{comb} \cdot TMV_{i,tp2}} \right) - \left(1 - \frac{\sum_{i \in SI_{cat,tp1=B}} SI_{long,i}^{comb} \cdot LMV_{i,tp1}}{\sum_{i \in SI_{cat,tp1=B}} SI_{long,i}^{comb} \cdot TMV_{i,tp1}} \right)$$

Important note regarding AMRA terminology:

AMRA uses non-standard variable names for the longitudinal composite results. These will be mapped to standard variable names for the analysis:

AMRA Variable:	Analysis Variable:
Reference Screening (TP1) at the Screening Visit	Study-level Baseline Value (BASE at Screening)
Reference Screening (TP1) at Visit Week xx	Visit-level Baseline Value (BASE at Visit Week xx)
Week xx (TP2) at Visit Week xx	Visit-level Actual Value (AVAL at Visit Week xx)

REACH TRIAL

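### In the supportive linear mixed model for whole-body MFI, a muscle lost to signal quality after Screening is counted as a change in MFI

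*SAP*

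**What the plan says.** SAP 9.3.1.5 lists four measures for the whole-body longitudinal composites.

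- **Baseline** is the reference composite recorded under the Screening visit: "Note that baseline is measured during screening".
- **Change from baseline** at Weeks 24 and 48 is a variable delivered by the MRI vendor.
- **Reference screening** is delivered separately at Weeks 24 and 48.
- **The absolute value** at follow-up is built from the last two: "Absolute for Y = Reference screening for Y at time t + Change from baseline for Y at time t".

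Appendix C explains why the reference can differ between visits. If a muscle newly fails signal quality, "the eligible muscle count will change and the Reference Screening values will be updated". A muscle dropped at one visit may return at a later one. The vendor's change score uses only muscles acceptable at both of the timepoints compared.

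SAP 10.2.2.2 makes the MMRM the primary analysis of this endpoint and adds an LME "where the dependent variable is absolute WB composite MFI, measured at baseline and each post-baseline visit". SAP 8.3.1 confirms that LMEs model the absolute measurement, with baseline as one of the response records, and derives an annualised percentage change from the slope and the intercept.

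On the baseline itself, the Appendix C text for the secondary endpoint calls the Week 48 reference value the baseline MFI. Its mapping table carries both a study-level baseline at Screening and a "Visit-level Baseline Value (BASE at Visit Week xx").

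**The concern.** The composite is a mean of muscle MFI weighted by lean muscle volume (LMV). Removing a muscle whose MFI differs from the rest moves that mean even if no muscle has changed. The vendor guards against this by recomputing the screening reference on the surviving muscles before taking the difference. The LME loses that protection: its first record comes from the full Screening set, and its later records come from whatever set survived at each visit.

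At stake are the LME outputs for MFI: the slope in each arm, the annualised percentage change in each arm, and the between-arm differences in both. The 9.3.1.5 derivations are common to MFI, MFF and LMV, so any LME on those other composites inherits the same feature.

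A smaller matter is that the MMRM includes baseline and baseline-by-visit terms, and no sentence says outright which of the two mapped baselines is the covariate.

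**Working it through.** **1. The plan's own figure.** SAP section 5 states that "a sample size of 210 patients with FSHD1 will provide at least 95% power with a 2-sided t-test at 0.025 significance level", with "assuming the within-group SDs are 0.72 and 1.0 respectively" (MFI is the first value) and a difference of 0.5. I read these in percentage points, the unit Appendix C gives for the change. With 105 per arm and 10% missing, 94.5 per arm are evaluable.

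- SE of the difference = 0.72 × √(2/94.5) = 0.1047
- 0.5 / 0.1047 = 4.77; the critical value at two-sided 0.025 is 2.24
- Power = Φ(4.77 − 2.24) = 99.4% (noncentral t also gives 99.4%)

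The claim of at least 95% is reproduced.

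**2. The artefact.** If a muscle with LMV share w is lost and nothing truly changes, the composite moves by

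shift = w × (MFI of the remaining muscles − MFI of the lost muscle).

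**3. Traced through the SAP rules** (assumed values: three B muscles, LMV 0.5, 0.4 and 0.1 L, MFI 12, 15 and 30%, no true change, third muscle fails at Week 48).

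- Screening composite = (0.5×12 + 0.4×15 + 0.1×30) / 1.0 = 15.0%
- Week 48 reference = (0.5×12 + 0.4×15) / 0.9 = 13.3%
- Vendor change = 0
- Week 48 absolute value = 13.3 + 0 = 13.3%
- The MMRM response is 0. The LME sees 13.3 − 15.0 = −1.67 points.
- Under the proposed derivation, 15.0 + 0 = 15.0%, and the artefact disappears.

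**4. Size per affected patient** (assumed: equal volumes, MFI evenly spaced over 11–35%, mean 23%, one muscle lost at random).

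| Muscles | Shift when muscle x is lost | Mean | SD | Largest |
|---|---|---|---|---|
| 12 | (23 − x)/11 | 0 | 0.68 | 12/11 = 1.09 |
| 20 | (23 − x)/19 | 0 | 0.38 | 12/19 = 0.63 |

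For 12 muscles the mean absolute shift is about 0.60. With unequal volumes, w = 0.05 and an MFI gap of 5 to 10 points gives 0.25 to 0.5; w = 0.10 and a gap of 5 to 20 points gives 0.5 to 2.0.

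**5. Size for the group, losses unrelated to treatment.** This is a two-sample approximation, not the LME itself. A fraction f of patients is affected, with shift SD s, so SD = √(0.72² + f·s²).

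| f | s | SD | Power at 0.025 |
|---|---|---|---|
| 0 | – | 0.72 | 99.4% |
| 10% | 1.0 | 0.79 | 98.3% |
| 20% | 2.0 | 1.15 | 77.4% |
| 100% | 0.68 | 0.99 | about 89% |

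**6. Selective losses.** If 10% of an arm each shift by −1.0 point, that arm's mean moves by 0.10 × (−1.0) = −0.10 points. If both arms are affected equally, this cancels in the difference but stays in each arm's slope.

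The documents give neither the rate of signal-quality failure nor the muscle mix, so items 3 to 6 show a range and are not estimates.

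**The case against.** The strongest reply is that the confirmatory result is untouched. The multiple-testing scheme in SAP 2.4.2 tests MFI once, and 10.2.2.2 assigns that role to the MMRM. Section 9.3.1.5 takes the change from the vendor's variable, and Appendix C computes it on muscles acceptable at both timepoints. A reader might infer that the alpha-protected test is compromised; the documents do not support that. This part of the reply stands in full.

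A reader might also infer that the SAP holds two irreconcilable baselines. Most of that reading falls away. Section 9.3.1.5 presents itself as covering the analysed dataset and Appendix C as an intermediate step. The Appendix C sentence that calls the Week 48 reference the baseline is offered in the vendor's terminology and describes what is subtracted in the change score. Loose wording remains: two mapped baselines and no explicit statement of the covariate. Also, the general rule in 9.2 (post value minus baseline), if applied with the Screening value, would not return the vendor's change when a muscle is lost.

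Finally, a reader might infer that muscle loss could dominate the MFI slope. That does not follow. The per-patient shifts in the 12- and 20-muscle examples average zero, no loss rate is given, and a shift in one patient is not comparable with a group difference of 0.5.

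The reply does not remove the LME mismatch itself. Using the visit-level baseline instead would not cure it, because one baseline record cannot match both Week 24 and Week 48 when their muscle sets differ.

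**Conclusion.** The point holds for the supportive LME only. As written, the SAP's rules build its MFI response from muscle sets that may differ between Screening and follow-up, so a signal-quality loss registers as MFI change in that patient.

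Under the assumed mixes, the shift in an affected patient runs from a few tenths of a point to about 2 points. For the between-arm comparison it is mainly added noise if losses are unrelated to treatment, and small unless losses are common or the shifts large. Within-arm slopes and annualised percentage changes would be distorted if losses fall selectively on fatter or leaner muscles. With no muscle lost, there is no effect.

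The MMRM test of MFI is not affected through its response. Its baseline covariate needs one clarifying sentence. This is a minor correction, worth making because it is cheap and removes an artefact that the vendor's own change score already avoids.

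**What to change.** - **LME derivation.** In SAP 9.3.1.5 and 10.2.2.2, set the Week 24 and Week 48 values for the LME to the Screening-visit composite plus the vendor's matched change at that visit. Apply the same rule to any LME on the MFF and LMV composites.
- **MMRM wording.** State in both 9.3.1.5 and Appendix C that the vendor's change score is the MMRM response, taking precedence over the general rule in 9.2, and that the Screening-visit composite is the baseline covariate.
- **Cross-reference.** SAP 9.3.3.2 sends the reader to 9.3.1.3 (study day) for this derivation; it should point to 9.3.1.5.

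The cost is SAP wording and one derivation line, with no new data. The downside is that the LME follow-up value becomes a constructed level, adding a change from the surviving muscles to a level from the full set, and is no longer the vendor's timepoint value. The latter can still be listed. An alternative is to fit the LME on a muscle set fixed across all visits.
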